### ***Primary safety outcomes***

Time point: end of month 3

The intervention of stepwise HD schedule will be considered safe, relative to standard HD schedule, if there will be no significant difference in severe adverse events between the two HD treatment groups during the first 3 months of the study.

Severe adverse event(s) will be defined as the requirement of one or more additional HD treatment(s) or hospitalization(s) for: (1) a condition related to poor volume control (i.e., clinically-determined volume overload, decompensated heart failure, or hypertensive urgency/emergency); (2) severe electrolyte imbalance (i.e., serum potassium  $>6.5\text{mEq/L}$ ); (3) severe metabolic acidosis (i.e., serum bicarbonate  $<15\text{mEq/L}$ ); (4) symptomatic uremia (i.e., uremic encephalopathy, uremic pericarditis); or (5) death associated with study intervention.

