## **Objectives**

The primary objective of this study is to evaluate the feasibility and safety of incremental HD in incident ESKD patients. The secondary objectives are to evaluate the effects of HD frequency on changes in RKF, clinical and laboratory parameters (i.e., volume management, solute clearance, hospitalization rate), quality of life, and patient survival.

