### **Sample Size**

The primary purpose of this pilot study is to evaluate the feasibility of a randomized intervention between a stepped regimen of HD and a standard regimen of HD. Therefore, for the primary feasibility outcome, we elect a pilot trial sample size of 50 patients total (25 patients per treatment group) which is consistent with recommendations for pilot and feasibility studies where samples of 10 to 20 participants per group have been deemed adequate to assess feasibility outcomes (Stat Methods Med Res 2016, 25(3), pp. 1057-1073). Power calculations for a future multicenter clinical trial will be carried out using the effect size on RKF and variability collected during this pilot study.

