For evaluation of primary safety end points and secondary clinical end points, intention-to-treat principles will be followed. Evaluation of categorical end points will be performed using chi-squared tests. Evaluation of continuous end points will be performed using Student's unpaired t-test for normally distributed variables, or the Wilcoxon rank-sum test for nonparametric data. For comparison of variables measured during the time course of the study, a repeated measures analysis of variance (ANOVA) will be used. The consistency of effects on the primary end point will be explored in a variety of subgroups. Kaplan–Meier methods will be used for time-to-first hospitalization analyses. Missing RKF data for subjects will be replaced (rather than excluding them from the analysis, as missing RKF measurements might not be completely at random) using linear regression to estimate values based on other measurements for each subject (linear trend at point, SPSS). For each group-sequential analysis, the upper bound of the one-sided confidence interval for the hazard ratio (incremental HD to conventional HD) would be calculated with the use of the critical value from the Lan–DeMets–O'Brien–Fleming alpha-spending function, which preserves an overall one-sided alpha of 0.025. No adjustments for multiplicity will be made. An independent Safety Monitoring Committee will review all available data on a quarterly basis. Analyses that signal safety concerns (i.e., higher rates of hospitalization, treatment failure or death in the intervention arm compared to the comparator arm) will be reported to an independent Steering Committee to determine whether the study should be discontinued, be modified and then proceed, or continue with caution.

Descriptive statistics will be used to report the results of Participant Feedback Questionnaire.

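### The primary safety rule reads a non-significant test at 25 patients per arm as proof of safety; 7/25 against 2/25 patients with severe adverse events would pass as safe

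*Combined protocol and SAP*

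**What the plan says.** The Objectives section makes safety one of two parts of the primary objective: "The primary objective of this study is to evaluate the feasibility and safety of incremental HD in incident ESKD patients".

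Primary safety outcomes gives the decision rule. The schedule "will be considered safe, relative to standard HD schedule, if there will be no significant difference in severe adverse events" between the arms "during the first 3 months of the study". The endpoint is defined in the same section: "Severe adverse event(s) will be defined as the requirement of one or more additional HD treatment(s) or hospitalization(s) for" a list of causes covering volume, potassium, acidosis and uremia, with intervention-related death also listed.

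The Analytical Plan supplies the test, "Evaluation of categorical end points will be performed using chi-squared tests", under intention-to-treat. It gives no significance level for it.

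The Sample Size section bases the number of patients on feasibility: "for the primary feasibility outcome, we elect a pilot trial sample size of 50 patients total (25 patients per treatment group". Power calculations are left to a future multicenter trial. No section gives a safety margin, power for the safety comparison or an expected control-arm event rate.

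**The concern.** A non-significant test shows only that the data did not rule out equal risk. It does not show that a harmful excess has been ruled out. In a small trial the two are far apart, and the smaller the trial, the easier this rule is to satisfy. Any shortfall in recruitment would make a finding of safety more likely.

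At stake is the pre-stated conclusion for one half of the primary objective. Human Subjects Protection classes the study as high risk and names fluid overload and raised potassium among the risks, and both fall within this endpoint. A label of safe obtained through low power could be carried into the planned larger trial.

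**Working it through.** **Inputs.** From the documents: 25 patients per arm (Sample Size), chi-squared test (Analytical Plan), 3-month endpoint (Primary safety outcomes). Assumed, because the documents do not say: the unit is the patient with at least one event, Pearson's test has no continuity correction, and the level is two-sided 5%. That level has the same critical value as the only alpha in the plan, one-sided 0.025. There is no safety power calculation to reproduce.

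**1. One example, no event rate assumed.** For 7/25 against 2/25, with N = 50:

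χ² = N(ad − bc)² / (n₁ n₂ m₁ m₂) = 50 × (7×23 − 2×18)² / (25 × 25 × 9 × 41) = 781,250 / 230,625 = 3.39, p = 0.066.

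With Yates' correction p = 0.141, and with Fisher's test p = 0.138. All three give a verdict of safe.

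Risk difference = 0.28 − 0.08 = +0.20. The Wilson limits are 0.143 to 0.476 (7/25) and 0.022 to 0.250 (2/25), so the Newcombe 95% limits are:
- lower: 0.20 − √[(0.280 − 0.143)² + (0.250 − 0.080)²] = −0.018
- upper: 0.20 + √[(0.476 − 0.280)² + (0.080 − 0.022)²] = +0.404

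**2. Largest intervention-arm count that still passes.**

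| Control events (of 25) | Largest passing intervention count (of 25) | p |
|---|---|---|
| 0 | 3 | 0.074 |
| 1 | 5 | 0.082 |
| 2 | 7 | 0.066 |
| 3 | 8 | 0.088 |
| 4 | 10 | 0.059 |
| 5 | 11 | 0.069 |

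**3. How often a truly worse schedule is declared safe.** P(safe) is the sum of Bin(a; 25, p_T) × Bin(b; 25, p_C) over all tables with p ≥ 0.05. The control rates are assumptions.

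| True rates, control v intervention | Declared safe |
|---|---|
| 10% v 20% (doubling) | 83% |
| 20% v 40% | 65% |
| 25% v 50% | 52% |
| 30% v 60% | 38% |
| 10% v 30% (tripling) | 55% |
| 15% v 45% | 33% |
| 20% v 60% | 13% |

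A true 20-point excess is declared safe 55% to 67% of the time at control rates from 10% to 40%. At lower control rates the rule does better: 44% for 5% v 25% and 34% for 2% v 22%. Power reaches 80% only at about 10% v 43% or 20% v 56.5%. Fisher's test is more permissive: 91% for 10% v 20%, 77% for 20% v 40% and 70% for 10% v 30%.

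**4. What 25 per arm can show.** With equal observed counts, the Newcombe upper 95% limit for the excess is +13 points at 0/25 v 0/25, +18 at 2/25 v 2/25 and +20 at 3/25 v 3/25.

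**The case against.** The best defence is that this is a feasibility pilot in which little depends on the label. Success is defined by four feasibility criteria (Primary feasibility outcome), and the Analytical Plan bases progression on those criteria. Quarterly safety review does not use this test, and the treating nephrologist may change dialysis frequency at any time. All of that stands, and it limits the harm to the safety conclusion. It does not justify the conclusion. Pilot status explains why the sample is small, not why a small sample should license a claim of safety.

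Second, the significance level and the unit of analysis are readings of an unspecified plan. A one-sided 5% test would flag 7/25 v 2/25 (p about 0.033). However, "if there will be no significant difference in severe adverse events between the two HD treatment groups" does not suggest a one-sided test, and the only stated alpha is one-sided 0.025. The example is also the boundary case against 2/25, as the table in the working shows.

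Third, at control rates of 5% or less, a 20-point excess is flagged more often than not under the uncorrected test. That is true, but 34% to 44% of such trials would still be called safe.

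Fourth, the Analytical Plan mentions a group-sequential criterion in which "the upper bound of the one-sided confidence interval for the hazard ratio (incremental HD to conventional HD) would be calculated". It names no endpoint, margin or number of looks and is not tied to the safety rule, so it does not supply what is missing.

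**Conclusion.** The concern holds, and the rule should be changed before the plan is used. Followed exactly, it can label a large observed excess as safe, and for a moderate true excess it would usually do so. A true doubling passes more often than not at control rates up to about 25%, and a true tripling up to about 11%.

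The boundary counts depend only on 25 per arm and the assumed patient-level, uncorrected, two-sided 5% test. The declared-safe percentages also depend on assumed control rates. Yates' correction or Fisher's test makes the rule weaker still.

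**What to change.** Delete the sentence that equates no significant difference with safety. Replace it with the following:

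- Report, for each arm, the number and proportion of patients with at least one severe adverse event by month 3.
- Report the risk difference (incremental minus conventional) with a two-sided 95% score-based confidence interval.
- State that the pilot estimates safety and cannot establish it, unless the upper limit lies below a margin fixed in advance.

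A margin is optional, and 25 per arm would support only a wide one. With equal true rates p, one-sided 0.025 and 80% power, n per arm = (1.96 + 0.84)² × 2p(1 − p) / margin². At a 10% event rate this gives 142 for a 10-point margin and 36 for a 20-point margin. At 5% it gives 75 and 19.

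As separate tidying, the hazard-ratio sentence in the Analytical Plan should either be tied to a named endpoint with stated looks or removed.

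The cost is wording only, with no new data or patients. The price is a more modest claim: with equal observed counts, the upper limit is at least +13 points. It would be lower only if the intervention arm had fewer events, for example about +9 points at 1/25 v 3/25.

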## **Methods and Measures**

### **Design**

This randomized pilot trial will be parallel-arm in design. We will enroll 50 patients of age  $\geq 18$  years, with incident ESKD. Participants will be equally randomized to one of the two regimens: a) twice-weekly HD plus adjunctive pharmacologic therapy (loop diuretic, potassium-binding agent, and sodium bicarbonate) for six consecutive weeks, continued by thrice-weekly HD (intervention group); or b) thrice-weekly HD (comparator group) (Appendix A). Patients will be followed for 12 months after the date of randomization; or until transplant, death, withdrawal of consent, or transfer of care outside Wake Forest healthcare system, whichever occurs sooner. Feedback from the participants will be obtained during the study to (1) evaluate the delivery of study-related information, (2) evaluate coordination of care during the study as it pertained to study-related procedures, (3) evaluate patient perceptions on study-related assessments, (4) elicit patients' motivations for study participation, and (5) obtain participant input regarding future research concerning the study intervention.

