*Diuretic therapy.* The use of diuretic agents increases sodium and water excretion and improves volume status in dialysis patients with RKF, and has been associated with maintenance of RKF. In an observational study from the Dialysis Outcomes and Practice Pattern Study, loop diuretic use was associated with lower interdialytic weight gain, lower odds of hyperkalemia, twice the odds of retaining RKF, and a 14% lower cardiac-specific mortality (Bragg-Gresham, Am J

Kidney Dis.2007). Start dose, Furosemide, 60-80mg orally/day if uncontrolled hypertension, no discernible peripheral edema, blood pressure stable, no symptoms of congestive heart failure; or Furosemide 80-120mg orally/day if peripheral edema and/or symptoms of congestive heart failure. Dose will be titrated as needed to control hypertension (goal SBP<140mmHg and/or DBP<90mmHg measured on inter-dialytic day or pre-HD) and manage signs and symptoms of volume overload to the best extent possible.

*Hyperkalemia treatment.* All patients will receive education for low potassium diet. It is expected that 25-30% of the patients in the intervention arm will require treatment for hyperkalemia. Treatment of hyperkalemia will be determined based on baseline serum potassium level available prior to HD initiation. Based on its proven efficacy and safety in clinical trials involving patients with CKD and hyperkalemia, patiromer will be prescribed as the potassium-binding agent of choice. Treatment with patiromer will be instituted for serum potassium levels of  $\geq 5.1$  mEq/L. Patiromer will be administered daily and during the study the dose will be adjusted, as needed, based on pre-HD serum potassium levels (Appendix B). The dose of patiromer will be titrated to maintain pre-HD serum potassium of 4.6 to 5.3 mEq/L. Patiromer will be withheld temporarily or stopped for pre-HD serum potassium levels of  $\leq 4.0$  mEq/L. Participants randomized to twice-weekly HD arm who were on a potassium binder prior study enrollment and HD initiation will be continued on patiromer (if on treatment with patiromer prior to enrollment) or switched to patiromer (if on a different potassium binder prior to enrollment). Participants randomized to thrice-weekly HD who were on a potassium binder prior study enrollment and HD initiation will have the potassium binder discontinued.

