### **Reporting of Unanticipated Problems, Adverse Events or Deviations** (Appendix D)

The principal investigator along with the research staff will be responsible for periodic evaluation of clinical trial data to ensure continued participant safety, protocol compliance, data collection as well as scientific validity. Adverse events are not anticipated, but any occurring will be documented and reported according to WFSM IRB policies and procedures. Cumulative adverse events and study progress summary will be communicated to the IRB at the time of continuing review.

Any unanticipated problems, serious and unexpected adverse events, deviations or protocol changes will be promptly reported by the principal investigator or designated member of the research team to the IRB.

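### Apart from intervention-associated death, the primary safety composite counts only harms of under-dialysis, so non-fatal admissions for hypokalemia, volume depletion or alkalosis cannot affect the month-3 safety conclusion

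*Combined protocol and SAP*

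**What the plan says.** Under Primary safety outcomes, the stepwise schedule is judged safe "if there will be no significant difference in severe adverse events between the two HD treatment groups during the first 3 months of the study". An event is the "requirement of one or more additional HD treatment(s) or hospitalization(s) for" one of five listed items:

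1. poor volume control: "clinically-determined volume overload, decompensated heart failure, or hypertensive urgency/emergency";
2. "severe electrolyte imbalance (i.e., serum potassium" above 6.5 mEq/L);
3. "severe metabolic acidosis (i.e., serum bicarbonate" below 15 mEq/L);
4. symptomatic uremia;
5. death associated with the study intervention.

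Under Design, the intervention arm receives "twice-weekly HD plus adjunctive pharmacologic therapy (loop diuretic, potassium-binding agent, and sodium bicarbonate) for six consecutive weeks", followed by thrice-weekly HD. The Hypothesis section describes the same package. Interventions and Interactions expects adjuvant drugs to be needed during the twice-weekly period, leaves dosing to the treating nephrologist, and says of the binder: "Patiromer will be withheld temporarily or stopped for pre-HD serum potassium levels of" 4.0 mEq/L or lower. A comparator patient already on a potassium binder has it stopped.

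Outside the composite, Data collection records every hospitalization and death with its cause. Secondary outcomes compares time to first hospitalization, cause and length of stay at end of follow-up. Data and Safety Monitoring has a Safety Officer review all hospitalizations quarterly.

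**The concern.** The randomized comparison is between two packages: fewer sessions plus three drug classes, against more sessions. The first four safety items look in one direction only. The drugs act in the other direction: they remove volume, lower potassium and raise bicarbonate. If one of them overshoots and the patient is admitted but survives, the primary safety outcome has no place for that event.

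At stake is what the word safe would mean at month 3. It would mean that no significant excess of under-dialysis events or intervention-associated deaths was seen. A reader would take it as a statement about the whole regimen, and it would probably be carried in that sense into the planned multicenter trial.

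**Working it through.** **Step 1. Definition against intervention.**

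| Domain | Counted in the composite | Not counted | Adjuvant drug |
|---|---|---|---|
| Volume | overload, heart failure, hypertensive crisis | volume depletion, hypotension | loop diuretic |
| Potassium | above 6.5 mEq/L | any low value | binder (hold level 4.0 or lower); loop diuretic |
| Acid-base | bicarbonate below 15 mEq/L | alkalosis | sodium bicarbonate |
| Uremia | encephalopathy, pericarditis | – | – |
| Death | if associated with the intervention | – | any |

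Four of the five items run only toward under-dialysis. The fifth has no direction, and because the drugs are part of the intervention it can register a drug-related death. The secondary biochemical and volume outcomes (hyperkalemia, metabolic acidosis, volume overload) run the same way as items 1 to 3.

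**Step 2. Where such an admission would be seen.** It would be seen in the secondary hospitalization outcome and in the quarterly review. Neither enters the month-3 rule. The secondary outcome is timed to end of follow-up, and its Kaplan–Meier analysis uses the first admission, so a drug-related second admission would not register there. Cause and length of stay are also compared.

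**Step 3. Exposure.** The protocol expects 25–30% of the intervention arm to need hyperkalemia treatment: 0.25 × 25 = 6.25 and 0.30 × 25 = 7.5, or about 6 to 8 patients. This counts patients treated, not patients harmed. No rate for hypokalemia, hypotension or alkalosis appears anywhere.

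**Step 4. What the omission could do.** The sample size of 50 (25 per arm) rests on recommendations for feasibility studies. No alpha, event rate or power is given for the safety comparison, so there is no planned figure to reproduce. The following rests on an assumed two-sided alpha of 0.05 and assumed rates.

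*A single hypothetical result.* Each arm has 2 of 25 patients with a listed event, and 6 further intervention patients are admitted for uncounted drug harms.
- As written: 2 v 2, chi-squared = 0.
- If counted: 8 v 2, chi-squared = 50 × (8×23 − 2×17)² / (25 × 25 × 10 × 40) = 50 × 150² / 250,000 = 4.5. This exceeds 3.84, p ≈ 0.034.

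By Fisher's exact test, 9 v 2 would be needed.

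*Chance of a significant excess in the intervention arm*, by summing binomial probabilities over all outcomes at 25 per arm:

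| Listed events, each arm | Added drug harm, intervention arm only | As written (chi-squared) | If counted (chi-squared) | If counted (Fisher) |
|---|---|---|---|---|
| 10% | 10 points | 2.4% | 17% | 8.5% |
| 10% | 20 points | 2.4% | 45% | 31% |
| 10% | 30 points | 2.4% | 73% | 59% |
| 20% | 10 points | 2.7% | 13% | 6.8% |
| 20% | 20 points | 2.7% | 35% | 23% |
| 20% | 30 points | 2.7% | 64% | 51% |

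The as-written column does not move with the drug-harm rate. The other columns show that counting these harms still leaves limited power. At a 10% base rate, 80% power would need about 199, 62 or 32 patients per arm for excesses of 10, 20 or 30 points. Even 0 events in 25 is compatible with a true rate of up to 1 − 0.025^(1/25) = 13.7% (two-sided 95% exact limit).

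**The case against.** The best defense is that the scope was chosen deliberately. The outcome is worded as a judgment on the HD schedule, and its items match the schedule risks listed under Human Subjects Protection. The nephrologist doses the drugs, with the protocol's schedules as guidance. Aiming a pilot's safety outcome at the main mechanism of harm is reasonable. That explains why items 1 to 4 are there. It does not explain leaving out the other direction, because Design makes the drugs part of what is randomized.

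A reader might infer more than the documents support:

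- *That drug harms are counted nowhere.* A related death counts in item 5, and every admission reaches the secondary comparison and the quarterly review. Under the Analytical Plan, higher hospitalization, treatment failure or death in the intervention arm goes to a Steering Committee.
- *That the omission favors the intervention.* This is plausible, since binder exposure differs by design. It is not shown. Both arms may receive drugs for volume overload and hypertension, and low potassium or hypotension can follow dialysis itself, of which the comparator has more.
- *That exposure measures the harm.* The bicarbonate start doses cover levels on both sides of 18 mEq/L, which might suggest all 25 patients are at risk. Treatment is tailored and given as and/or, so 25 is only an upper bound on exposure.
- *That "Adverse events are not anticipated" shows that drug harms are ignored.* The same sentence goes on to require that any event be documented and reported.

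If the i.e. in item 2 was meant as e.g., severe hypokalemia might already qualify. As written it does not.

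**Conclusion.** The point stands in a limited form. Non-fatal hospitalizations for hypokalemia, volume depletion or hypotension, and metabolic alkalosis contribute zero events to the primary safety composite at any rate, although the regimen being judged includes drugs that act in those directions. This follows from the text and needs no assumption. How much it matters cannot be derived from the documents. The chances in the working depend on assumed rates, an assumed alpha and the assumption that all added harm falls in the intervention arm. The direction of any bias remains unproven. This should be corrected before the month-3 analysis, but the trial is not without other safety oversight.

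**What to change.** In Primary safety outcomes, add hospitalization for hypokalemia, for volume depletion or hypotension, and for metabolic alkalosis to the severe adverse event definition, scored identically in both arms. The clinical team should set any laboratory thresholds. State whether item 2 is meant to be limited to high potassium. Beside the composite, report all-cause and cause-specific hospitalizations by arm at month 3 with confidence intervals.

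Do not tabulate potassium at or below 4.0 mEq/L from all available results. Data and Safety Monitoring has results reviewed at least weekly in the intervention arm and twice monthly in the comparator, so detection would be unequal. If low potassium is shown, use only scheduled measurements common to both arms. Keep the new items to hospitalizations, because unplanned treatment outside hospital is not among the data listed for collection.

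The cost is a change of outcome wording and one table, since all admissions are already recorded with cause. The event count may become less favorable to either arm. The change does not repair the low power of a no-significant-difference rule at 25 per arm.

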### **Interventions and Interactions**

Screening for potential participants will be performed at the outpatient nephrology clinics, outpatient dialysis units, inpatient nephrology service, and inpatient dialysis unit of Wake Forest Baptist Medical Center. The decision to initiate RRT is not part of the study; initiation of RRT will be deemed by patient's nephrologist. After patient's nephrologist decided that initiation of RRT is medically necessary, the overall eligibility for enrollment in this study will be reached as a consensus between the PI and the patient's nephrologist, based on the aforementioned inclusion and exclusion criteria. After written informed consent is obtained, participants will be allocated with equal probability to either incremental HD (intervention) or conventional HD (comparator) strategy. Allocation to incremental or conventional HD will be done using randomly permuted

blocks of varying sizes, stratified by the type of vascular access used at HD initiation, to maintain balance between the groups.

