Dialysis prescription (HD treatment time and frequency of administration, achieved blood flow, dialysate flow, potassium and calcium dialysate baths), vascular access used for HD, target weight (TW), inter-dialytic weight gain (IDWG), and ultrafiltration rate (UFR) will be recorded throughout the study. Relative IDWG will be expressed as percentage of TW when divided by the nephrologists' determined target weight. All hospitalizations and deaths (along with the cause) will be recorded from the time of enrollment to study end.

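### The month-3 safety composite counts a death only if it is linked to the study intervention, with no stated rule for controls or for who decides, so an unlinked death can be scored as event-free

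*Combined protocol and SAP*

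**What the plan says.** All references are to the combined protocol and SAP.

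- **Primary safety outcomes.** The stepwise schedule is declared safe "if there will be no significant difference in severe adverse events between the two HD treatment groups during the first 3 months". A severe event is defined as the "requirement of one or more additional HD treatment(s) or hospitalization(s) for" a list of reasons: poor volume control, severe electrolyte imbalance, severe acidosis, symptomatic uraemia and, as the fifth item, "death associated with study intervention".
- **Interventions and Interactions.** Patients are allocated to "incremental HD (intervention) or conventional HD (comparator) strategy". The Design section labels the arms in the same way.
- **Sample Size.** "50 patients total (25 patients per treatment group").
- **Analytical Plan.** On the analysis set, the plan says: "For evaluation of primary safety end points and secondary clinical end points, intention-to-treat principles will be followed". The test is named in a separate sentence: "Evaluation of categorical end points will be performed using chi-squared tests".
- **Data collection.** "All hospitalizations and deaths (along with the cause) will be recorded from the time of enrollment to study end".
- **Exploratory outcome.** Mortality is compared between the two schedules at the end of follow-up.
- **Data and Safety Monitoring.** An unblinded Safety Officer reviews hospitalizations quarterly. The study team follows the intervention arm, and the usual nephrologists follow the comparator arm.

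The text available does not define associated, does not say who makes the attribution, and does not say how an unattributed death before month 3 enters the composite.

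**The concern.** A between-arm safety comparison needs an event that can be scored in the same way in both arms. A test of association with the study intervention is hard to apply to a patient on conventional thrice-weekly dialysis. One assessor might never attribute a control death. Another might read the phrase as the assigned regimen and attribute it readily. Dialysis frequency is visible to everyone, so an attribution may also be made with knowledge of the arm.

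The consequence falls on patients who die without an earlier qualifying event, for example suddenly at home. Unless the death is attributed, they stay in the intention-to-treat denominator as event-free. With few events expected, one such decision can move the result across the significance threshold on which the safety verdict rests.

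A smaller point is that the list places death under reasons for an extra dialysis session or admission, where it does not fit.

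**Working it through.** The plan gives no event rate, mortality rate, margin or power for the safety composite, so there is no figure of its own to reproduce. What follows measures how sensitive the verdict is.

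**Inputs from the protocol:** 25 patients per arm (Sample Size); chi-squared test (Analytical Plan); safe if the difference is not significant (Primary safety outcomes).

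**Assumptions:** two-sided 5% level and no continuity correction, since neither is stated for this test; three-month mortality of 1% to 8%; where needed, a 10% risk of a non-fatal composite event in each arm.

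**1. Weight of one death.** 1/25 = 4 percentage points of an arm's risk.

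**2. Effect of one attribution on the verdict.** With a events in the incremental arm and b in the control arm, z = [(a − b)/25] / √[p(1 − p) × 2/25], where p = (a + b)/50.

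- 8 vs 2: z = 0.24/√(0.20 × 0.80 × 0.08) = 0.24/0.1131 = 2.12, p = 0.034, so not declared safe.
- 7 vs 2 (one incremental-arm death judged unrelated): z = 0.20/√(0.18 × 0.82 × 0.08) = 0.20/0.1087 = 1.84, p = 0.066, so declared safe.
- In the other direction, 8 vs 3: z = 0.20/√(0.22 × 0.78 × 0.08) = 0.20/0.1172 = 1.71, p = 0.088, so declared safe. If one of the three control events is a death that cannot be attributed, the table becomes 8 vs 2, p = 0.034, so not declared safe.

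The tables at which the verdict flips depend on the version of the test. With a continuity correction or Fisher's exact test, 8 vs 2 is already non-significant (p = 0.077 and 0.074). The flip then occurs between 9 vs 2 (p = 0.041 and 0.037) and 8 vs 2. The sensitivity to a single event remains.

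**3. How many deaths might be in play.** Expected deaths are 50m, and the chance of at least one is 1 − (1 − m)^50.

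| Assumed mortality m | Expected deaths | Chance of at least one |
|---|---|---|
| 1% | 0.5 | 39% |
| 2% | 1.0 | 64% |
| 3% | 1.5 | 78% |
| 5% | 2.5 | 92% |
| 8% | 4.0 | 98% |

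These are chances of any death. A misclassified death must also be left unattributed and have no qualifying event before it. The documents give no basis for that probability.

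**4. Direction.** I enumerated all outcomes at 25 per arm. The composite risk is 0.10 + 0.90 × (counted death risk).

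- Equal mortality of 8%, all deaths counted: 0.10 + 0.90 × 0.08 = 0.172 in both arms. A significant result against the incremental arm occurs in 2.7% of trials. If every incremental-arm death is attributed and no control death is (0.172 vs 0.10), it occurs in 11.5%. If half the incremental-arm deaths are attributed (0.136 vs 0.10), it occurs in 6.0%.
- True mortality of 20% vs 4%: counting all deaths (0.28 vs 0.136) flags harm in 25.1% of trials. If no death is attributed (0.10 vs 0.10), harm is flagged in 2.4%.

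The full-attribution and no-attribution cases are extremes, chosen to show that the error can go either way.

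**The case against.** The strongest reply has five parts.

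1. **One definition is written for both arms.** A reader might infer that the plan sets a different death definition for each arm. The text does not go that far. Sample Size and Analytical Plan use intervention loosely enough to cover either regimen, so death linked to the assigned regimen is a possible reading. Design, Interventions and Interactions, and the opening of Primary safety outcomes point to the incremental arm. The supportable word is ambiguous.
2. **Unblinded attribution is not stated.** A reader might take it as fact that deaths are judged with knowledge of the arm. The Safety Officer's unblinded review is described for hospitalizations, and no section assigns attribution of deaths to anyone. Appendix D, whose title includes cause of death, is not in the text available and may contain a rule. This limb is an inference.
3. **Deaths are not lost to the trial.** They are recorded with cause and compared as an exploratory outcome. The Safety Monitoring Committee reviews all available data quarterly, and a higher death rate in the incremental arm is escalated without a relatedness filter. This is correct, but none of it enters the month-3 rule.
4. **All-cause death has a price.** The other components are specific to inadequate dialysis. Unrelated deaths can dilute a real difference, and under a rule of no significant difference that makes a declaration of safety easier. This stands, and the fix allows for it.
5. **The stakes are limited.** The sample size was chosen for feasibility, and progression rests on four feasibility criteria that do not include this composite. That limits the consequence, but safety remains a primary outcome with an explicit verdict, in a study that the protocol itself rates as high risk.

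The misplaced list item is a drafting slip. Read sensibly, death is meant as a separate event, so the wording alone does not show a design flaw.

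**Conclusion.** The concern holds as an undefined and potentially asymmetric attribution test within the primary safety composite. Followed as written, an unattributed death with no earlier qualifying event is scored event-free, and a control death has no clear route into the count. One such decision is worth 4 percentage points of an arm's risk and can reverse the verdict in either direction.

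Two further readings go beyond the documents. The 39% to 98% chance of at least one death is not the chance of a misclassified one, and it rests on an assumed mortality of 1% to 8%. Nor can the rule be said to favour the incremental arm: over-attribution there makes it look worse, and under-attribution hides harm. The p-values assume an uncorrected two-sided test at 5%, and the enumeration also assumes a 10% non-fatal event risk.

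This should be changed before the safety comparison is made. It does not affect the feasibility conclusions.

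**What to change.** - In Primary safety outcomes, make death from any cause by month 3 a stand-alone component in both arms, outside the list of reasons for extra dialysis or admission.
- Add a supportive analysis of the composite that counts only deaths related to the assigned regimen. State one attribution rule for both arms and name the assessor, preferably one who is unaware of the arm. If Appendix D already holds such a rule, refer to it and confirm that it applies to controls.
- State in Analytical Plan which version of the chi-squared test is used, because the threshold tables differ.

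**Cost.** The component itself is a wording change, since deaths and causes are already recorded. The attribution rule adds a small adjudication task. The statistical downside is noise and possible dilution from unrelated deaths, which is why both versions should be reported side by side.
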